8.1.1 Inclusion criteria

- ◆ Documented relapsed/refractory CLL or SLL requiring treatment according to IWCLL criteria (no limits on previous treatment lines; CD20 and steroids are not considered prior therapy lines).
- ◆ Age at least 18 years.
- ◆ Adequate bone marrow function defined as:
 - Absolute neutrophil count (ANC) $>0.75 \times 10^9/L$
 - Platelet count $>30,000 /\mu L$ $30 \times 10^9/L$.
 - Hemoglobin $>8.0 \text{ g/dL}$ (5 mmol/L)Unless directly attributable to CLL infiltration of the bone marrow, proven by bone marrow biopsy
- ◆ Creatinine clearance (CrCL) $\geq 30 \text{ ml/min}$ calculated according to the modified formula of Cockcroft and Gault or directly measured with 24hr urine collection.
- ◆ Adequate liver function as indicated
 - Serum aspartate transaminase (AST) or alanine transaminase (ALT) $\leq 3.0 \times$ upper limit of normal (ULN)
 - Bilirubin $\leq 1.5 \times$ ULN (unless bilirubin rise is due to Gilbert's syndrome or of non-hepatic origin)
 - Prothrombin time (PT)/International normal ratio (INR) $<1.5 \times$ ULN and PTT (activated partial thromboplastin time [aPTT]) $<1.5 \times$ ULN (unless abnormalities are related to coagulopathy or bleeding disorder).
- ◆ Negative serological testing for hepatitis B (HBsAg negative and anti-HBc negative; patients positive for anti-HBc may be included if PCR for HBV DNA is negative and HBV-DNA PCR is performed every month until 12 months after last dose), negative testing for hepatitis C RNA within 42 days prior to registration.
- ◆ WHO/ECOG performance status 0-3 (appendix C), stage 3 only if attributable to CLL.
- ◆ Negative pregnancy test at study entry (for women of childbearing potential).
- ◆ Male and female subjects of reproductive potential must agree to use both a highly effective method of birth control (e.g. implants, injectables, combined oral contraceptives, some

intrauterine devices [IUDs], complete abstinence , or sterilized partner) and a barrier method (e.g., condoms, cervical ring, sponge, etc.) during the period of therapy and for 90 days after the last dose of study drug.

- ◆ Ability and willingness to provide written informed consent and to adhere to the study visit schedule and other protocol requirements.
- ◆ Written informed consent.

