- cervical (head and neck, including Waldeyers ring, involvement of more than one group of nodes counts as one area)
- axillary (involvement of both axillae counts as one area)
- inguinal lymphadenopathy (including superficial femorals, involvement of both groins counts as one area)
- splenomegaly
- hepatomegaly

B. Response criteria

(Halek et al, 2008)

Response assessment will be based on the revised guidelines of the international workshop on CLL (IWCLL); these are as follows (see table on the next page) – a separate manual will be supplied to indicate the exact response assessment guidelines.

Complete remission (CR)¹ :

All below listed criteria must be fulfilled and no disease related symptoms should be present.

Complete remission with incomplete recovery of the bone marrow (CRi)¹:

All below listed criteria must be fulfilled, except for an incomplete recovery of the bone marrow with persisting anemia, thrombocytopenia and/or neutropenia (related to toxicity of treatment and not due to CLL) and no disease related symptoms should be present.

Partial response (PR):

Among the below listed criteria at least 2 from group A and 1 from group B must be fulfilled.

PR lymphocytosis:

PR without a 50% decrease in blood lymphocytes

Stable disease (SD):

Failure to achieve a PR and absence of PD.

Progressive disease (PD):

Presence of at least 1 of the below enlisted criteria or appearance of new lymph nodes >1.5cm, hepato- or splenomegaly or organ infiltration by CLL.

Relapse:

progressive disease more than 6 months after PR/CR was reached.

¹ A clinical CR/CRi fulfills the same criteria as a CR or CRi but was not (yet) confirmed with a bone marrow examination.

Parameter	CR	Cri	PR	PD
Group A (indicating tumor load)				
Lymphadenopathy ¹	none >1.5cm		decrease ≥50%	increase by ≥50% or new lymph nodes ≥1.5cm
Hepatomegaly	None		decrease ≥50%	increase by ≥50%
Splenomegaly	None		decrease ≥50%	increase by ≥50%
Blood lymphocytes	<4000/μl		decrease of ≥50% from baseline	increase by ≥50% over baseline to ≥5000/μl
Bone marrow	normocellular	hypocellular	50% reduction in BM infiltrates ²	irrelevant
	<30% lymphocytes, no B-lymphoid nodules			
Group B (indicating function of the hematopoietic system)				
Platelet count	≥100000/μl	Irrelevant	≥100000/μl or increase by ≥50% from baseline	decrease by ≥50% due to CLL
Hemoglobin	>11g/dl (6.8 mmol/L)	Irrelevant	>11g/dl or increase by ≥50% from baseline	decrease by > 2g/dl (1.2 mmol/L)

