Neutrophil count	>1500/ml	Irrelevant	>1500/ml or increase by ≥50% from baseline	

¹ Assessed as sum of the products of multiple lymph nodes, if available an indicator lymph node (the largest palpable) from every region should be compared in every staging.

² In case of B-lymphoid nodules a 4-colour-flow cytometry is recommended to clarify if this is related to CLL, if flow cytometry is negative these patients can be rated as CR/CRi, if all other criteria are fulfilled

C. ZUBROD-ECOG-WHO Performance Status Scale

- 0 Normal activity
- 1 Symptoms, but nearly ambulatory
- 2 Some bed time, but to be in bed less than 50% of normal daytime
- 3 Needs to be in bed more than 50% of normal daytime
- 4 Unable to get out of bed
- 5 Death

D. Common Terminology Criteria for Adverse Events

The grading of adverse events will be done using the NCI Common Terminology Criteria for Adverse Events, CTCAE version 4.0. A complete document may be downloaded from the HOVON website:

<http://www.hovon.nl> (under Trials > General information about studies)

E. Modified Cockcroft Gault Formula for Calculated Creatinine Clearance (CrCl)

For Serum creatinine concentration in mg/dl:

$$\text{CrCl} = \frac{(140 - \text{age}(\text{yr})) \times (\text{IBM}) \times (0.85 \text{ if female, or } 1.0 \text{ if male})}{72 \times \text{serum creatinine (mg/dL)}} \quad (\text{ml/min})$$

For Serum creatinine concentration in $\mu\text{mol/L}$:

$$\text{CrCl} = \frac{(140 - \text{age}(\text{yr})) \times (\text{IBM}) \times (1.23 \text{ if male, or } 1.04 \text{ if female})}{\text{serum creatinine } (\mu\text{mol/l})} \quad (\text{ml/min})$$

$$\text{IBM (kg)} = [(\text{height in cm} - 154) \times 0.9] + (50 \text{ if male, } 45.5 \text{ if female})$$

F. Cumulative illness rating scale (CIRS)**The Modified Cumulative Illness Rating Scale (CIRS)**

Please take into account that CLL induced illness or organ damage are not included in this rating scale.

Body system	Score				
1. Cardiac (heart only)	0	1	2	3	4
2. Hypertension (rating is based on severity; organ damage is rated separately)	0	1	2	3	4
3. Vascular (blood, blood vessels and cells, bone marrow, spleen, lymphatics)	0	1	2	3	4
4. Respiratory (lungs, bronchi, trachea below the larynx)	0	1	2	3	4
5. EENT (eye, ear, nose, throat, larynx)	0	1	2	3	4
6. Upper GI (esophagus, stomach, and duodenum; pancreas; do not include diabetes)	0	1	2	3	4
7. Lower GI (intestines, hernias)	0	1	2	3	4
8. Hepatic (liver and biliary tree)	0	1	2	3	4

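### Protocol Appendix B gives the neutrophil threshold for CR and PR per ml instead of per µl, so read literally it can hardly ever fail

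*Protocol*

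**What the plan says.** Appendix B (Response criteria) defines response by a table in two groups. Group A covers tumor load; Group B covers platelets, hemoglobin and neutrophils.

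- **PR rule:** "Among the below listed criteria at least 2 from group A and 1 from group B must be fulfilled".
- **CR rule:** every listed criterion must be met.
- **CRi rule:** as for CR, "except for an incomplete recovery of the bone marrow with persisting anemia, thrombocytopenia and/or neutropenia", where the cytopenia comes from treatment toxicity and not from CLL.
- **Platelets, PR cell:** "≥100000/μl or increase by ≥50% from baseline".
- **Lymphocytes, PD cell:** "increase by ≥50% over baseline to ≥5000/μl".
- **Neutrophils, PR cell:** ">1500/ml or increase by ≥50% from baseline". The CR cell has the same threshold and unit without the alternative. The CRi cell is marked as irrelevant, and no PD criterion is given.

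Elsewhere ANC is stated in 10^9/L: above 0.75 for entry (section 8.1.1) and below 0.5 for grade 4 neutropenia (Appendix H).

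Section 10.4 refers to the IWCLL guidelines for the response definitions and to Appendix B for a tabular summary. Appendix B also announces a separate manual with the exact assessment rules.

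**The concern.** The neutrophil row is the only cell-count row in the table not given per µl, and the difference is a factor of 1000. A threshold that low does not discriminate.

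Two rules depend on it. PR asks for one Group B item out of three, and an item that is always met satisfies that condition for everyone. CR differs from CRi by recovery of the blood counts and marrow, and a neutrophil line that cannot fail removes one of the cytopenias that the CRi definition names.

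The table feeds CR/PR/SD at six time points (cycles 3, 9, 12 and 15, months 27 and 51) and duration of response (section 13.2). It also feeds the split into PR or better versus less than PR, which section 14.4.5 gives as an example of a covariate in the quality-of-life model.

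**Working it through.** **1. Check the conversion on the protocol's own pairs.** Per µl x 10^6 = per L; per ml x 10^3 = per L.
- Section 8.1.1, platelets: 30,000/µl x 10^6 = 30 x 10^9/L, as paired there.
- Platelets in Appendix B: 100,000/µl x 10^6 = 100 x 10^9/L, the same figure as Binet stage C in Appendix A.

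**2. Convert the neutrophil threshold.**
- As written: 1500/ml x 10^3 = 1.5 x 10^6/L = 0.0015 x 10^9/L, or 1.5 cells/µl.
- With the unit of the other cell-count rows: 1500/µl x 10^6 = 1.5 x 10^9/L.
- Ratio: 1.5 / 0.0015 = 1000.

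**3. Compare with the protocol's other ANC limits.**
- Entry: 0.75 / 0.0015 = 500.
- Grade 4: 0.5 / 0.0015 = 333.

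**4. Apply the absolute threshold to a range of counts** (setting aside the alternative of a 50% rise).

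| ANC (10^9/L) | Meets >1500/ml | Meets >1500/µl |
|---|---|---|
| 0.05 | yes | no |
| 0.1 | yes | no |
| 0.3 | yes | no |
| 0.5 | yes | no |
| 0.75 | yes | no |
| 1.0 | yes | no |
| 1.4 | yes | no |
| 1.6 | yes | yes |

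Even 0.05 x 10^9/L is 50,000/ml, about 33 times the written limit. Only a count at or below 1.5 cells/µl would fail. The second half of the PR cell, a rise of at least 50%, then has almost nothing left to do, which is a further sign that the unit is not the intended one.

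**5. Who is reclassified by the correct unit?**
- *PR to a lower category:* a patient who meets two Group A items but fails platelets, hemoglobin and neutrophils, each including its 50%-rise alternative. Without progression, that patient becomes SD. If any one Group B item is met under the correct unit, nothing changes.
- *CR to CRi:* a patient who meets every other CR criterion and has treatment-related neutropenia as the only shortfall. Anemia, thrombocytopenia or a hypocellular marrow already separates CRi from CR as the table stands.

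**6. Does it reach the primary endpoint or randomization?**
- No neutrophil criterion for PD is given, so progression does not depend on this row.
- After reinitiated treatment, section 13.1 accepts at least SD as response, and sections 7 and 9.4 also count SD.
- Randomization requires at least SD (section 8.2).

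None of these uses the neutrophil threshold.

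**The case against.** The strongest reply is that nobody will apply the row literally. Section 10.4 makes the cited guideline the source and Appendix B its summary; a manual is promised; the CRi text names neutropenia; and any hematologist would recognize the slip. That limits the practical harm and is a good reason not to rate the point highly. It does not make the table right. Section 10.4 points readers to Appendix B for the criteria, and neither the manual nor the guideline is available here to show that the unit is corrected.

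A second reply is that the PDF reading may have turned µ into m. This cannot be excluded. However, the sign is read correctly in the other cell-count rows and /ml appears in both neutrophil cells, so an error in the source is more likely. The page should be checked first.

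A third reply, that the effects are narrow, stands in full (step 5). Three stronger inferences are tempting and should not be drawn:

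- **A large distortion of CR.** A reader might take the grade 3 or higher neutropenia rates in section 9.7.1 (36.0% and 41%) as the share mislabelled. They are occurrence rates from venetoclax monotherapy studies and a 17p-deletion study, not neutropenia at assessment among patients otherwise in CR on this regimen. The listed endpoint also names CR, PR and SD without CRi, so it is not stated whether a move between CR and CRi changes the reported CR rate.
- **An effect of the CR/CRi exchange on the quality-of-life covariate.** Both categories are better than PR, so only the PR effect can reach it.
- **A need to rewrite the PR rule for SLL.** A reader might add that patients with nodal disease only cannot easily meet two Group A items. That is a separate question from the unit. The documents do not supply an exception to the two-item rule, and removing a marrow item that cannot be met would change no classification under a rule that asks for at least two.

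**Conclusion.** The unit is wrong as written, subject to the check of the source page. The error is exactly 1000-fold and makes the neutrophil criterion one that practically every patient meets. Read literally, Group B no longer restricts PR, and neutropenia alone no longer distinguishes CRi from CR.

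The consequence is limited to secondary response endpoints and, through PR, the quality-of-life covariate. Sections 14.4.3 and 14.4.6 treat these analyses as hypothesis-generating. The primary endpoint, its test and the randomization are unaffected. The number of patients reclassified cannot be derived from the protocol. It depends on how many fail all three Group B items or have neutropenia as their only shortfall, and on whether the table is applied literally.

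**What to change.** 1. Check the source page to rule out a µ/m reading error.
2. If the page does read /ml, change both neutrophil cells (CR and PR) to >1500/µl, i.e. 1.5 x 10^9/L, in line with the other cell-count rows.
3. Confirm that the response manual and any programmed derivation of response use the same unit, and reconcile them if they do not.

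The cost is two table cells and a check of the related material. No new data and no change to design or sample size are needed. CR and PR rates may fall slightly in patients with persisting cytopenia.

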14.4.4 Interim analysis

No interim analysis on the primary endpoint is planned.

Draft outline of interim analyses in the study:

Analysis	Time point	Analysis	Impact on primary endpoint
Analysis IA	First 15 pt. after induction cycle 3	Interim analysis on safety	No, only safety
Analysis IB	First 10 pt. with low CrCl 30-50. After induction cycle 3.	Interim analysis on safety	No, only safety
Analysis II	first 23 pt. reaching MRD negativity at cycle 9 or first 51 pt. at cycle 9, which occurs first	Interim analysis on safety and efficacy	No impact, prior to randomization
Analysis III	15 pt. randomized for stopping treatment after cycle 15 or first 51 pt. at end of cycle15, which	Interim analysis on safety and efficacy	No impact, at time of randomization

	occurs first		
Analysis IV	6 months after first 15 pt. randomized for stopping treatment at cycle 15 or 6 months after first 51 pt. at cycle 15, which occurs first	Interim analysis on efficacy	Post randomization, MRD positivity and primary are dependent. No correction.
Analysis V	12 months after 15 pt. randomized for stopping treatment at cycle 15 or 12 months after first 51 pt. at cycle 15, which occurs first	Interim analysis on efficacy	Post randomization, MRD positivity and primary are dependent. No correction
Analysis VI	Last patient reaching Month 27	Primary end point analysis	
Analysis VII	Last patient reaching 7 years	Update final analysis	

In the Interim analyses on safety (IA and IB), , the incidence of (serious) adverse events, death, creatinine level, AEs of special interest (atrial fibrillation, bleeding events and TLS) and progression according to appendix B and MRD positivity, will be reported. These analyses will be before the randomization stage and patients have not been assigned to any of the arms.

In Interim analysis on safety and efficacy and In Interim analysis on efficacy, the incidence of (serious) adverse events, death, creatinine level, number of assigned patients at each treatment arm, number of progression, best response, number of reinitiated patients (if applicable), AEs of special interest (atrial fibrillation and bleeding events), TLS)and progression according to appendix B and MRD positivity, will be reported.

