Potassium	≥ 6.0 mmol/L (≥ 6.0 mEq/L) or 25% increase from baseline
Phosphorous	≥ 1.45 mmol/L (≥ 4.5 mg/dL) or 25 % increase from baseline
Calcium	≤ 1.75 mmol/L (≤ 7.0 mg/dL) or 25% decrease from baseline

Laboratory tumor lysis syndrome (LTLS) is defined as either a 25% change or level above or below normal, as defined above, **for any two or more serum values** of uric acid, potassium, phosphate, and calcium within 3 days before or 7 days after the initiation of chemotherapy. This assessment assumes that a patient has or will receive adequate hydration (± alkalinization) and a hypouricaemic agent(s) (Cairo, 2004).

Clinical Tumor Lysis Syndrome (CTLs):

Clinical tumor lysis syndrome (CTLs) assumes the laboratory evidence of metabolic changes and significant clinical toxicity that requires clinical intervention

The presence of LTLS and one or more of the following criteria:
Creatinine: ≥ 1.5 ULN *
Cardiac arrhythmia / sudden death*
Seizure *

*) Not directly or probably attributable to a therapeutic agent (e.g. rise in creatinine after amphotericin administration). (Cairo, 2004)

Cairo-Bishop Tumor Lysis Syndrome Grading

#	Grade 0	Grade 1	Grade 2	Grade 3	Grade 4	Grade 5
LTLS	-*	+	+	+	+	+
Creatinine [#]	≤ 1.5 x ULN	1.5 x ULN	> 1.5-3.0 x ULN	> 3.0-6.0 x ULN	> 6.0 x ULN	Death [§]
Cardiac arrhythmia [#]	None	Intervention not indicated	Nonurgent medical intervention indicated	Symptomatic and incompletely controlled medically or controlled with device (e.g., defibrillator)	Life-threatening (e.g., arrhythmia associated with CHF, hypotension, syncope, shock)	Death [§]
Seizure [#]	None	-	One brief, generalized seizure; seizures(s) well controlled by anticonvulsants; or infrequent focal motor seizures not interfering with ADL	Seizures in which consciousness is altered; poorly controlled seizure disorder, with breakthrough generalized seizure despite medical intervention	Seizures of any kind which are prolonged, repetitive, or difficult to control (e.g., status epilepticus, intractable epilepsy)	Death [§]

CTLs requires one or more clinical manifestations along with criteria for LTLS

Maximal CTLs manifestation (renal, cardiac, neuro) defines the grade

* No LTLS

Not directly or probably related to a therapeutic agent

§ Attributive probably or definitely to CTLs

Further actions need to be taken in case of:

- potassium increase by ≥ 0.5 mmol/l from baseline and/or any potassium value > 5.0 mmol/l

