Blood chemistry changes or symptoms suggestive of TLS (Cairo-Bishop grading in Appendix G)	Any	Withhold the next day's dose. If resolved within 24-48 hours of last dose, resume at the same dose.
		For any blood chemistry changes requiring more than 48 hours to resolve, resume at one dose level reduction
		For any events of clinical TLS, resume at one dose level reduction following resolution
Non-Hematologic Toxicities		
Grade 3 or 4 non-hematologic toxicities	1 st occurrence	Interrupt venetoclax Once the toxicity has resolved to Grade 1 or baseline level, venetoclax therapy may be resumed at the same dose. No dose modification is required.
	2 nd and subsequent occurrences	Interrupt venetoclax. Restart at one dose level reduction when resuming treatment with venetoclax after resolution. A larger dose reduction may occur at

Event	Occurrence	Action
		the discretion of the investigator.
Hematologic Toxicities		
Grade 3 or 4 neutropenia with infection or fever; or Grade 4 hematologic toxicities (except lymphopenia)	1 st occurrence	Interrupt venetoclax. To reduce the infection risks associated with neutropenia, granulocyte-colony stimulating factor (G-CSF) may be administered with venetoclax if clinically indicated. Once the toxicity has resolved to Grade 1 or baseline level, venetoclax therapy may be resumed at the same dose.
	2 nd and subsequent occurrence	Interrupt venetoclax. Consider using G-CSF as clinically indicated. Restart at one dose level reduction when resuming treatment with venetoclax after resolution. Additional dose reductions may occur at the discretion of the physician.

Patients who require dose reductions to less than 100 mg for more than 4 weeks should stop treatment.

Management of Neutropenia

Nonclinical and clinical experience indicates that venetoclax may cause neutropenia. Subjects with a history of neutropenia who have received multiple prior therapies and/or have significant bone marrow involvement may be at a particularly high risk.

Grade 3 or 4 neutropenia has been reported in patients treated with venetoclax. Complete blood counts should be monitored throughout the treatment period. Dose interruptions or dose reductions are recommended for patients with severe neutropenia. Supportive measures including antimicrobials for any signs of infection and prophylactic use of growth factors(e.g. G-CSF) should be considered.

Management of Hematologic Toxicities Other Than Neutropenia or Lymphopenia

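### The clinical-TLS creatinine item in Appendix G has no baseline reference, so some patients admitted with CrCl 30-50 ml/min can meet it before any venetoclax

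*Protocol*

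**What the plan says.** Appendix G adopts the Cairo-Bishop criteria. Laboratory TLS needs two or more abnormal values and "is defined as either a 25% change or level above or below normal, as defined above", so its four electrolyte and uric acid items can be met through change from baseline. Clinical TLS is laboratory TLS plus at least one of three items: creatinine, arrhythmia or sudden death, or seizure. The creatinine item reads "Creatinine: ≥ 1.5 ULN". The footnote to all three items exempts only events that are "Not directly or probably attributable to a therapeutic agent (e.g. rise in creatinine after amphotericin administration". The grading table also uses multiples of ULN: creatinine above 1.5 and up to 3.0 x ULN is grade 2.

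The sentence introducing these criteria says: "Clinical tumor lysis syndrome (CTLs) assumes the laboratory evidence of metabolic changes and significant clinical toxicity that requires clinical intervention".

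Section 8.1.1 admits patients with CrCl of at least 30 ml/min, "calculated according to the modified formula of Cockcroft and Gault or directly measured with 24hr urine collection". It sets no ceiling on serum creatinine. Section 9.1 admits CrCl 30-50 ml/min on conditions, one of which acts on a creatinine increase above 15%; that rule is not linked to the TLS definition. Section 14.4.4 plans analysis IB on "First 10 pt. with low CrCl 30-50" ml/min and lists TLS and creatinine level among the items reported. Appendix I, Table I1 states: "For any events of clinical TLS, resume at one dose level reduction following resolution".

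**The concern.** A criterion meant to mark renal injury from tumor lysis is written as a level that a patient may have at entry. For such a patient the renal item is satisfied throughout, and any laboratory TLS becomes clinical TLS automatically. An unchanged entry creatinine is hard to square with "significant clinical toxicity that requires clinical intervention", so the list of criteria and its lead-in point in different directions.

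Two things are at stake. First, the mislabelling is concentrated in patients with low CrCl, whose safety analysis IB is meant to examine, so TLS there can look more severe than it was. Second, Table I1 treats clinical TLS differently from blood chemistry changes that resolve quickly, so the label alone can decide which row applies.

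**Working it through.** **Inputs from the protocol.** Appendix E, for creatinine in µmol/L: CrCl = (140 - age) x IBM x k / creatinine, with k = 1.23 for men and 1.04 for women, and IBM = (height in cm - 154) x 0.9 + 50 for men or 45.5 for women. The printed constants are consistent with the mg/dL version: 88.4/72 = 1.228 and 0.85 x 88.4/72 = 1.044. The inversion below applies where CrCl is calculated; for a 24-hour urine measurement the formula does not fix the creatinine.

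**Assumptions.** The protocol gives no ULN and no age, height, sex or CrCl distribution. The base case here is ULN 105 µmol/L for men and 90 for women, giving limits of 157.5 and 135 µmol/L.

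**Step 1: one patient.** Man aged 68, 178 cm: IBM = 24 x 0.9 + 50 = 71.6 kg. Creatinine = 72 x 71.6 x 1.23 / CrCl = 6340.9 / CrCl. This gives 211, 181, 159 and 127 µmol/L at CrCl 30, 35, 40 and 50. At CrCl 35 his stable value of 181 is 1.72 x ULN, already in the grade 2 range. He crosses the limit at CrCl 6340.9 / 157.5 = 40.3 ml/min.

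**Step 2: CrCl at or below which the item is already met.**

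| Patient | (140 - age) x IBM x k | Crossing CrCl (ml/min) |
|---|---|---|
| Man 60 y, 176 cm | 80 x 69.8 x 1.23 = 6868.3 | 43.6 |
| Man 70 y, 176 cm | 70 x 69.8 x 1.23 = 6009.8 | 38.2 |
| Man 80 y, 176 cm | 60 x 69.8 x 1.23 = 5151.2 | 32.7 |
| Woman 60 y, 164 cm | 80 x 54.5 x 1.04 = 4534.4 | 33.6 |
| Woman 70 y, 164 cm | 70 x 54.5 x 1.04 = 3967.6 | 29.4 |

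The item is therefore reachable at entry for men over part of the 30-50 range. From about age 70, a woman of this height does not reach it anywhere in that range.

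**Step 3: share of the CrCl 30-50 subgroup already at the level (simulation).**

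- CrCl uniform over 30-50, age 70 (SD 9), height 176/163 cm (SD 7): 41% of men and 8% of women. At two men to one woman, (2 x 41 + 8)/3 = 30%. Moving ULN by 10 µmol/L either way gives 27-59% of men and 3-18% of women.
- CrCl uniform, mean age 70, mean height 178/165 cm, 65% men: 33% overall (46% of men, 9% of women).
- The same, but with CrCl weighted toward 50: 19% overall.
- Entry creatinine lognormal, then CrCl 30-50 selected: about 3-14% overall at ULN 105/90.
- All assumptions tried (ULN 100-115 for men and 80-97 for women; mean age 65-75): about 2% to 55%. The top needs mean age 65, uniform CrCl and the lowest ULN.

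**Step 4: where the label matters.** Under Table I1, chemistry changes that take more than 48 hours to resolve lead to the same one-level step as clinical TLS. Only laboratory TLS that resolves within 48 hours moves to a different row because of the label.

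**Step 5: scale in analysis IB.** With 10 patients, one relabelled patient moves a clinical-TLS proportion by 10 percentage points. If 5-20% develop laboratory TLS (an assumption) and 30% of those are already at the level, the expected number relabelled is 10 x 0.05 x 0.30 = 0.15 to 10 x 0.20 x 0.30 = 0.6 patients.

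**The case against.** The strongest reply is that Appendix G uses a published scale unmodified, and that its lead-in already qualifies the creatinine item: no significant toxicity, no clinical TLS. The footnote's own example is a rise in creatinine. This is a fair reading, but the protocol does not say that the lead-in overrides the criteria. The footnote exempts only drug attribution, and the grading row follows the absolute level. Two sites could score the same patient differently, so the request to reconcile stands.

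Other parts of the reply succeed and limit the point:

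- **Reporting.** A reader might infer that analysis IB will report an overstated clinical-TLS rate. Section 14.4.4 names TLS, not clinical TLS, and no comparison with other patients or threshold on such a rate is defined. IB also reports creatinine level, so the DSMB would see the value concerned.
- **SAE counts.** Section 12.3.1 makes every TLS case an SAE, so relabelling leaves SAE counts unchanged.
- **Resolution.** A reader might infer that a patient with chronically raised creatinine could never satisfy the Table I1 wording on resolution. The definition does not support that: clinical TLS requires laboratory TLS, so it lapses once the laboratory abnormalities resolve.
- **Frequency.** A reader might infer that this affects many low-CrCl patients. The documents contain no figure for this, and under most assumptions tried it is a minority, with few older women.

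**Conclusion.** The point holds in limited form. As written, the creatinine item and its grading row are absolute and do not exempt stable renal impairment. Some admitted patients with CrCl 30-50 ml/min can therefore be scored as clinical TLS, grade 2 or higher, on laboratory TLS alone. That the item can be met at entry follows from the protocol's own formula once a plausible ULN is assumed. How often it is met cannot be fixed from the protocol: about 2% to 55% of the subgroup under the assumptions shown, and the share bears only on patients who go on to develop laboratory TLS.

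The practical effect is on the apparent severity of TLS in the group reviewed in IB, and on the Table I1 row when chemistry resolves within 48 hours. The primary endpoint is not involved. In 10 patients the expected number affected is below one, but a single case would be conspicuous in so small a group.

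**What to change.** In the safety analyses (IA, IB and later), tabulate TLS by the published grading and, beside it, with the creatinine item counted only when it is new or worsened against the pre-venetoclax value. Under the second tabulation, a patient above the level before dosing who does not rise remains laboratory TLS unless another clinical item is present. Appendix G already requires serum creatinine before each ramp-up dose, so no new data are needed. The cost is a derivation rule and one extra table; the small downside is that the second tabulation departs from the published scale, which is why both should be shown.

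Separately, the sponsor should reconcile four texts: the clinical-TLS criteria and grading row in Appendix G, the sentence that introduces them, the creatinine-increase rule in section 9.1, and the clinical-TLS row of Table I1. Which clinical or dosing rule should apply is for the sponsor; none is proposed here.
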